### **6.2 Exclusion criteria:**

- allergy or contraindication to ketamine
- unable or refused to receive a neuraxial or regional nerve block
- patient refusal
- direct transfer from operating room to ICU with endotracheal tube placed
- treating team elects to exclude the patient prior to study drug administration
- abortion of surgical procedure

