### **7. Enrollment/randomization:**

Patients presenting for elective major abdominal surgery at VUMC are automatically screened to receive care within our enhanced recovery program. Patients are approached on the day of their surgery by a physician member of our Perioperative Medicine team, who describes our goals, multimodal pathways, and obtains consent to perform a regional nerve block. Eligible patients will be consented for inclusion in the trial during this initial encounter; patients returning for a follow up procedure that meets inclusion criteria will be reapproached for consent and rerandomized as appropriate. Consent for the trial will be included as an adaptation to our current consent form for neuraxial or regional nerve block procedures, with the addition of the following language:

“Vanderbilt University Medical Center (VUMC) is a learning healthcare system where we evaluate how well our routine treatments and interventions for pain control work after surgery and possible side effects they may produce. As part of your perioperative care, you will receive a bundled approach of different pain regimens that have been shown to work both alone and together to relieve pain. At VUMC, we are studying different aspects of our routine bundled pain regimen to determine the most effective parts and combinations.

If you are eligible for enrollment in a study about treatment of your pain, you may be assigned to one of multiple routinely used regimens to help control your pain. Upon enrollment, you will be randomized to receive either a ketamine or saline infusion. We are doing this study to understand which regimens have better pain control and fewer side effects in different patients. You will have pain medicine available as you need it regardless of the regimen used. Potential side effects of those pain medicines include confusion, sleepiness, agitation, slowing of your breathing, and changes in blood pressure. Data will be collected from your medical record to evaluate how well your pain

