## 8. Study procedures:

Procedure/Activity	Frequency
Patient randomization	Randomization will occur in clusters of one week. All patients in the same week will receive the same therapy (ketamine or placebo), with the choice being determined by a pre-generated random sequence.
intraoperative ketamine bolus (0.5mg/kg) vs placebo followed by continuous infusion 5 mcg/kg/min	once
postoperative ketamine infusion (2.5 mcg/kg/min, up to 100kg max) vs placebo for 48 hours	once
electronic medical record chart review	for data capture and statistical review

Data will be abstracted from the EMR. Some data will be obtained through the Research Derivative. The Research Derivative is a database of clinical and related data derived from the Medical Center's clinical systems and restructured for research. Data is repurposed from VU's enterprise data warehouse, which includes data from StarPanel, VPIMS, and ORMIS (Operating Room Management Information System), EPIC, Medipac, and HEO among others. The medical record number and other person identifiers are preserved within the database. Data types include reimbursement codes, clinical notes and documentation, nursing records, medication data, laboratory data, encounter and visit data, among others. Output may include structured data points, such as ICD 9 codes or encounter dates, semi-structured data such as laboratory tests and results, or unstructured data such as physician progress reports. The database is maintained by the Office of Research Informatics under the direction of [name].

**Due to a national shortage of ketamine, study enrollment was paused on April 3rd, 2023 and then resumed on September 18th, 2023.**

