## **12. Statistical considerations including sample size justification (power analysis) and statistical analysis plan (optional at this stage for investigators not versed in statistical methodology):**

This study is a cluster randomized, pragmatic clinical trial. Initial analysis will use descriptive statistics and data visualizations to both identify and address spurious values, and to characterize the study cohort. Characteristics will be grouped by study arm, but we do not plan to compare the study arms with statistical tests.

The primary outcome is length of stay, measured in days. It is expected that length of stay is a skewed distribution, and so non-parametric methods are preferred. However, it

is not possible to consider the clustering or baseline covariates using a Wilcoxon test. Therefore, a proportional odds regression model will be used. Clustering will be taken into account using a mixed-effects model. If there are patients included twice because they underwent two elective major abdominal surgeries, patient will also be included as a random effect. The model will include baseline characteristics such as age, BMI, history of substance use (smoking status and opioid status if available), and type of surgical procedure. The common odds ratio from the model will be estimated; this quantity can be interpreted similar to the concordance probability and is robust to the proportional odds assumption. We will also report the model-assisted estimands of mean and median length of stay. Bootstrapping will be used to generate appropriate confidence intervals.

We will use an intention to treat analysis and all participants who are randomized will be included in the statistical analysis and analyzed according to group assignment. Participants will be removed from the analysis if their provider deems the patient ineligible prior to study drug administration. If a participant or provider withdraws the participant from the study following study drug administration, the participant will receive care at the provider's discretion, but will remain in the statistical analysis.

The secondary outcomes will be explored in a similar way. The proportional odds model will be used to evaluate differences in opioid use in the hospital. Occurrence of events will be reported as rates with confidence intervals. Logistic regression will be used to compare the odds of events between groups.

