Adult patients presenting on a weekday for an elective major inpatient abdominal surgery at VUMC will be screened for eligibility. Indications for exclusion will be noted if they meet criteria specified in the study protocol. Two post-randomization exclusions have been prespecified for this study. First, a patient directly transferred from the operating room to the Intensive Care Unit (ICU) with an endotracheal tube placed will not be included. The rationale is that these patients are exposed to both a sedative and narcotic infusion for the duration of their intubation, which would confound the ability to determine analgesic efficacy and/or side effects from the study drug. Furthermore, Enhanced Recovery After Surgery (ERAS) protocols are not followed in the ICU, and therefore there would be significant deviations from study protocol. Importantly, we aim to study ketamine's effects within ERAS principles for specifically elective surgeries. A transfer to the ICU while intubated reflects the occurrence of a major, unintended, and unanticipated intraoperative event for these elective procedures. The focus for that patient is no longer expedited recovery, but rather life-sustaining measures. Second, abortion of planned surgical procedure will qualify as a post-randomization exclusion. These patients do not undergo the intended surgical experience, will have different care pathways and goals, and are often discharged prior to 48 hours (length of time for the intervention). This exclusion will be defined as the patient being discharged home within 23 hours of anesthesia stop time, consistent with an 'observation' status rather than 'inpatient admission' to the hospital. Manual chart review will be performed to ensure appropriate exclusion. The occurrence of these exclusions will be tracked between study arms. Eligible patients will be consented for inclusion in the trial usually on the day of their surgery; patients returning for a follow up procedure that meets inclusion criteria will be reapproached for consent and rerandomized as appropriate.

Cohort Definition for Data Analysis

Intent-to-Treat Cohort

Intent-to-treat cohort includes all participants who are eligible and did not meet exclusion criteria specified in the study protocol.

Per-Protocol Cohort

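### The SAP's intent-to-treat cohort is a modified ITT cohort: it drops patients after consent into an assigned week, one rule turns on discharge time, and no planned analysis includes them

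*SAP*

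**What the plan says.** Protocol section 12 announces an intention-to-treat analysis in which "all participants who are randomized will be included in the statistical analysis and analyzed according to group assignment". The next sentence makes one exception: "Participants will be removed from the analysis if their provider deems the patient ineligible prior to study drug administration". The sample-size text in the same section then adds 30 patients for two pre-specified post-randomization exclusions.

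The SAP uses the same label for a different set: "Intent-to-treat cohort includes all participants who are eligible and did not meet exclusion criteria specified in the study protocol". The criteria it points to are in protocol section 6.2. They include "direct transfer from operating room to ICU with endotracheal tube placed", abortion of the procedure, "treating team elects to exclude the patient prior to study drug administration", and being unable or refusing to have the nerve block.

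The SAP's Study Population section declares only the first two of these as post-randomization exclusions, gives a rationale for each, and says they will be tracked by arm. It identifies an aborted procedure by discharge home within 23 hours of anesthesia stop, with manual chart review to check the exclusion.

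On timing, protocol section 8 assigns whole weeks from a sequence generated beforehand. Protocol section 7 says "Patients are approached on the day of their surgery by a physician member of our Perioperative Medicine team", and trial consent is taken at that encounter.

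The SAP's Main Analysis section uses the intent-to-treat cohort. The only alternative cohort is per-protocol.

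**The concern.** A reader told that the analysis is intent-to-treat will assume that everyone assigned is analysed. Here the arm is fixed before the patient is approached, so any exclusion applied after consent is applied after assignment. Intubated transfer to the ICU is known only at the end of surgery, once intraoperative study drug has begun. The 23-hour rule is known only at discharge, the event that ends the primary outcome. Read literally, it could remove a completed operation followed by a very fast recovery, which is the benefit the trial hopes to show.

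If assignment changed who was excluded, the retained arms would no longer be comparable. The tracked counts would show an imbalance, but not what it did to LOS. The ICU-transfer outcome also leaves out direct transfers from the operating room, so the tracked count is the only planned record of the intubated cases.

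**Working it through.** **1. The plan's own figure.** 1514 + 30 = 1544, as stated. The allowance is 30/1544 = 1.9%. It covers only the two declared exclusions, and the documents do not give the mix.

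**2. The exclusions side by side.**

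| Exclusion in protocol 6.2 | When it can apply | Exception stated in protocol 12 | Declared in SAP as post-randomization, tracked by arm | In the 30 |
|---|---|---|---|---|
| Intubated transfer, OR to ICU | After intraoperative study drug has started | Only through the sample-size text | Yes | Yes |
| Aborted procedure | Found through discharge time, then chart review | Only through the sample-size text | Yes | Yes |
| Treating team, before study drug | After consent, before drug | Yes | No | No |
| Block not possible or refused | Can follow consent | No | No | No |

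The sentence about all randomized participants therefore conflicts with three of the four rows unless it is qualified. The per-protocol cohort is defined by completion or tolerance of the infusion and is not described as restoring any of these patients.

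**3. How far the estimate could move.** These are illustrations, not bounds. Assumptions not in the documents: 757 retained per arm with identical LOS (no true effect), ICU stays at M = 2 to 4 times the average, aborted stays at 0.2 times the average. With i ICU and a aborted patients put back in an arm,

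mean = (757 + i·M + 0.2·a) / (757 + i + a), in units of average LOS.

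The concordance column ranks ICU stays highest, aborted stays lowest and retained patients equal. The odds ratio column is from a simplified proportional odds fit (20 equal LOS categories, no covariates or random effect).

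| Patients put back, arm 1 vs arm 2 | Ratio of means, M = 2 to 4 | Concordance | Odds ratio |
|---|---|---|---|
| Balanced | 0 | 0 | 1.00 |
| ICU 10:5, aborted 10:5 | +0.1 to +1.4% | 0 | 1.00 |
| ICU 10:5, aborted even | +0.65 to +1.9% | +0.003 | 1.02 |
| ICU 10:5, aborted 5:10 | +1.2 to +2.4% | +0.006 | 1.04 |
| All ICU, 20:10 | +1.25 to +3.7% | +0.006 | 1.04 |
| All aborted, 20:10 | -1.0% | -0.006 | 0.96 |

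Swapping the arms reverses the signs.

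**4. Scale.** The documents do not state the sample-size method. Assume a two-sided rank comparison with design effect DE = 1 + (m - 1)(0.014). The standard error of the concordance is then 1/sqrt(3·1514/DE).

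- m = 15: DE = 1.196, SE = 0.0162, detectable shift (1.960 + 1.036) × SE = 0.0486.
- m = 20: DE = 1.266, SE = 0.0167, detectable shift = 0.0500.

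The largest illustrated shift, 0.0064, is 0.0064/0.0162 = 0.39 SE (0.38 at m = 20), or about 13% of the detectable shift.

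**5. The opposite starting point.** Suppose instead that all 772 per arm have equal mean LOS and 20 are removed from one arm and 10 from the other. The retained ratio is [(772 - 20k)/752] / [(772 - 10k)/762], where k is the excluded patients' LOS relative to the average. It is 0.986 at k = 2, 0.972 at k = 3 and 1.011 at k = 0.2. So removing more short stays from one arm makes that arm look slightly slower.

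**6. What chance alone does.** If assignment has no influence on exclusion, a split of 10:5 or worse among 15 has two-sided probability 0.30, and 20:10 or worse among 30 has 0.10. Splits of this size are ordinary sampling variation. They do not show that the retained comparison is biased.

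**The case against.** The strongest reply is that the two main exclusions are open and reasoned. They appear in the protocol's criteria, in both sample-size texts and in the SAP, which ties them to a question about elective surgery under ERAS care. Patients and providers are blinded, charts are reviewed and counts are kept by arm. That stands, and it is why the cohort can remain primary.

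Treating-team exclusion is also defensible. Protocol section 12 states it directly after the general sentence, and it precedes study drug under blinding, so the drug cannot have caused it in that patient. What is left is a mismatch: the SAP neither lists it with its declared post-randomization exclusions nor provides a count by arm.

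A reader might infer from step 3 that the planned estimate is biased. The documents do not support that. Bias needs assignment to alter who is excluded, and neither document describes such a route. In that set-up the retained patients give the correct null, and it is the restored patients that move the estimate.

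A reader might also infer that fast recoveries will in fact be removed. The planned chart review suggests that the 23-hour rule may serve as a screen rather than the whole test. But the SAP does not say what the review must confirm, or whether it is done blind to arm.

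**Conclusion.** The point holds as one of labelling, reconciliation and a missing check. The SAP's cohort is modified ITT, it conflicts with the general sentence in protocol section 12, and no planned analysis includes the dropped patients. The aborted-procedure definition deserves most attention because it conditions the analysis set on the time that ends LOS.

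Any bias is potential and probably small. The declared exclusions are expected to affect about 1.9% of patients; the numbers excluded by the treating team or for the block are not given. The largest illustrated shift on the primary scale is about 0.006 in concordance, roughly 0.4 standard errors. That figure rests on assumed LOS multipliers, assumed splits and an assumed rank-test standard error. It shows how far the estimate could move, not that it has moved. Power is not at issue. This is a minor point.

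**What to change.** - Reconcile protocol sections 6.2 and 12 (the analysis-set and sample-size text) with the SAP's Study Population and cohort sections, and call the cohort modified ITT. It may stay primary for its ERAS rationale.
- Define the aborted-procedure exclusion as abandonment of the planned operation, confirmed from the chart by someone blind to arm. Use discharge within 23 hours only to find charts for review.
- Report every post-consent exclusion by arm and reason, including treating-team and block exclusions and direct intubated ICU transfers.
- Pre-specify one sensitivity analysis: the same primary LOS model in all consented patients, analysed by their week's assignment, with LOS from the EMR and without those who refuse use of their data.

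The cost is some wording, a few more rows in the exclusion table, a short blinded chart check and one extra model run on data from a source already in use. The downside is that a few heterogeneous stays enter the sensitivity analysis only. No larger sample is needed.

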**4.2 Secondary Outcomes:**

- a) total consumption of inpatient opioids in morphine milligram equivalents
- b) surgical outcomes including rapid response, transfer to icu, and ileus
- c) the incidence of side effects, including hallucinations, sedation, adverse reactions requiring early cessation

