**Statistical Analysis Plan for the Effect and Contribution of a Perioperative Ketamine Infusion in an
Established Enhanced Recovery Pathway**
[name], [name], and [name]

Version 1.0
September 6, 2023
NCT04625283
IRB #200210

Principal Investigator: [name] [name]

Key Study Personnel:

[name] [name]
[name]
[name], BS
[name]
[name], MS
[name], MS
[name]
[name], MS
[name]
[name]
[name], MS
[name]
[name]
[name], NP
[name], MSc
[name], BS, CCRP
[name], BA

Introduction

This document describes the statistical analysis plan (SAP) for a cluster randomized, pragmatic clinical trial studying the effect of ketamine within a pre-established enhanced recovery program on patients presenting for elective major abdominal surgery. Each week is considered a cluster with each cluster being randomly assigned to either the control or intervention condition.

Opioid consumption during the perioperative period is associated with adverse outcomes. In efforts to decrease opioid exposure after surgery, medical providers at Vanderbilt University Medical Center (VUMC) employ a multi-modal approach to pain control, which includes strategic combinations of non-narcotic pain medications and regional nerve blocks. Evidence is clear that combinations of non-narcotic pain medications with different mechanisms of actions are synergistically effective. What is not known, however, is the individual contribution of each medication to the overall efficacy of the regimen. This trial intends to explore the contribution of ketamine and hypothesizes patients randomized to receive ketamine will have a significant reduction in length of stay (LOS), following anesthesia start, compared to those receiving placebo.

Study Population

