To better understand the potential efficacy of ketamine, a per protocol cohort will be analyzed which will include patients in both arms who did not have the study infusion stopped for adverse effects. The per-protocol cohort includes participants who finished the 48-hour post-operative infusion (either ketamine or placebo), as well as participants for whom the study infusion was intentionally discontinued early because the patient met appropriate recovery milestones and was preparing for discharge. However, this per-protocol cohort will exclude any patients in whom the study infusion was stopped for intolerance or side effects, including those patients who were discharged prior to 48 hours but had the post-operative study infusion stopped prior to 48 hours due to intolerances or side effects.

Treatment Arms

Randomization of treatment arms will occur in clusters of one week so that all patients in the same week will receive the same therapy (i.e., ketamine or placebo).

- A. **Intervention:** Patients will receive a weight-based (up to 100 kg max) intraoperative ketamine bolus (0.5 mg/kg) followed by continuous infusion (5 mcg/kg/min), and an additional postoperative ketamine infusion (2.5 mcg/kg/min, up to 100 kg max) for 48 hours.
- B. **Placebo:** Patients will receive an intraoperative saline bolus followed by continuous infusion of equivalent volume to study drug dosed for 5 mcg/kg/min, and an additional postoperative saline infusion for 48 hours at an equivalent volume of infusion as the intervention arm.

Outcomes

Primary Outcome

The primary outcome is the LOS in days for the placebo arm and the intervention (ketamine) arm. LOS is defined as the time between anesthesia start and the patient being discharged (patient physically leaving the hospital).

Secondary Outcomes

1. Total consumption of post-enrollment inpatient opioids in morphine milligram equivalents during the perioperative period to hospital discharge
2. The incidence of following surgical outcomes:
 - a. rapid response team calls
 - b. transfer to ICU (not including direct transfer from OR to ICU as these patients are excluded from the study) after patient has been sent to the PACU or floor
3. The incidence of the following indications or side effects requiring early cessation of the study medication, as documented by the provider at the time of discontinuing the order (from Best Practice Advisory, BPA)
 - a. Meeting milestones/preop for discharge

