 - b. Mild side effects, but prefers discontinuation
 - c. Debilitating hallucinations
 - d. Debilitating dizziness
 - e. Hemodynamic instability
 - f. Other severe side effect

4. The incidence of ileus requiring gastric decompression as defined by orogastric or nasogastric tube placement in the postoperative period

Exploratory Outcomes

1. Instances of reoperation within the index encounter
2. VUMC hospital readmissions within 30 days post-discharge (not including ED visits)

Design Considerations

Randomization

Randomization will occur in clusters of one week. All patients in the same week will receive the same therapy (ketamine or placebo), with the selection being determined by a pre-generated random sequence.

Power and Sample Size

We anticipate the use of ketamine will reduce LOS following surgery start. To determine how long this trial will need to run to have sufficient power to detect a meaningful difference, we assumed 85% power, a type I error rate of 5%, and a 10% reduction in LOS. We estimated the within period correlation from preliminary data concerning the length of stay for major abdominal surgeries to be about 0.014. Given these assumptions, about 1514 patients would need to be included overall. An increase in sample size is necessary to accommodate for the two post-randomization exclusions that are pre-specified. We expect approximately 30 participants to be impacted by these post-randomization exclusions and will therefore increase the sample size by 30 to account for this exclusion (n=1544). Given surgical volumes, we expect 20 patients to be enrolled each week, and for the trial to last approximately 18 months.

Statistical Approach

Descriptive Analysis

We will describe the study cohort both overall and by treatment arm. To characterize the study sample, demographic and clinical data will be described. Categorical variables will be described using frequencies and proportions; continuous variables will be described using means and standard deviations as well as medians and interquartile ranges (IQR). Missingness will be recorded for each variable. To further assess the distribution of variables, graphical summaries will be displayed using graphs such as boxplots, dotplots, and/or histograms. No statistical testing will be performed to compare characteristics between groups. At a minimum, the following baseline variables will be described:

- Age (years)
- Sex assigned at birth (male, female, unknown)
- Race
 - Caucasian

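### Opioid use is totalled only to discharge, so the plan cannot tell lower opioid need from fewer days in hospital; add one prespecified 48-hour total

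*SAP*

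**What the plan says.** The SAP (Secondary Outcomes, item 1) defines the opioid outcome as "Total consumption of post-enrollment inpatient opioids in morphine milligram equivalents during the perioperative period to hospital discharge". Section 4.2 of the protocol gives no window: "total consumption of inpatient opioids in morphine milligram equivalents". The primary outcome, LOS, runs from anesthesia start until the patient leaves the hospital, so both outcomes close at the same event. The SAP (Power and Sample Size) states the expected direction: "We anticipate the use of ketamine will reduce LOS following surgery start".

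The postoperative part of the intervention has a fixed length: "an additional postoperative ketamine infusion (2.5 mcg/kg/min, up to 100 kg max) for 48 hours". The SAP Introduction states the gap the trial is meant to fill: "What is not known, however, is the individual contribution of each medication to the overall efficacy of the regimen".

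The opioid total is analysed with a mixed-effect proportional odds model using the primary model's covariates, with no term for time in hospital. The one sensitivity analysis of this outcome changes the cohort (per-protocol), not the window. No fixed-window or per-day opioid measure appears among the secondary, exploratory or sensitivity analyses of either document.

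**The concern.** The opioid window closes at an event that treatment is expected to move. Two things then affect the total besides opioid need.

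- **Fewer days.** If ketamine shortens the stay and opioids are still being taken on the days removed, the total falls even when use per day is unchanged.
- **Later use.** Opioids given after the 48-hour infusion add to both arms. If ketamine acts only during the infusion, its relative (or rank) effect on the total is diluted. The absolute MME difference is not reduced, only made noisier.

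This matters because the trial asks what ketamine itself contributes. No pain score is listed as an outcome, so total MME is the planned outcome that bears most directly on analgesic effect. Two ketamine trials summarised in protocol section 5 used fixed 24-hour opioid totals, which the planned result would not match directly.

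**Working it through.** **1. What the plan's own figures provide.** No figure is given for the opioid outcome. For LOS, "we assumed 85% power, a type I error rate of 5%, and a 10% reduction in LOS", with a within-period correlation of 0.014, 20 patients per week and 1514 patients. No mean or SD is stated, so 1514 cannot be rebuilt forward, but the spread it implies can be solved for.

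- Design effect: 1 + (20 − 1) × 0.014 = 1.266.
- Linear scale, two-sided: N = 4 (1.960 + 1.036)² CV² / 0.10² × 1.266 = 1514 gives CV ≈ 0.58.
- Log scale, with ln(0.9) as the effect: log-SD ≈ 0.61.
- Check against the protocol's 20% scenario (370): the linear scale gives 1514 / 4 ≈ 379; the log scale gives 1514 × (ln 0.9 / ln 0.8)² ≈ 338.

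The sample size is roughly consistent on the linear scale. It says nothing about opioids; it only suggests a plausible LOS spread.

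**2. Assumptions for the opioid total.** LOS is lognormal with median 3, 4 or 5 days and log-SD 0.61 (0.54, the lognormal equivalent of CV 0.58, changes little). Opioid rate at time t in days is exp(−ct), with c = 0 (constant), 0.3 or 0.6. For simplicity the 48-hour window is counted from the start of the stay.

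- Mean total to discharge: T = E[(1 − e^(−cL))/c], or E[L] when c = 0.
- Mean 48-hour total: W = the same with min(L, 2) in place of L.
- Stay 10% shorter, rate unchanged: replace L by 0.9L.
- True 20% reduction confined to 48 hours, stay unchanged: apparent reduction in the total = 20% × W/T.

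Example (median 4, c = 0.3): T = 2.282 falls to 2.174, or 4.7%. W = 1.466, so a true 20% shows as 20% × 1.466 / 2.282 = 12.8%.

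| Median LOS | c | Fall in total, LOS −10% | Fall in 48 h total, LOS −10% | True 20% early effect shows as | Share of MME after 48 h |
|---|---|---|---|---|---|
| 3 | 0 | 10.0% | 2.3% | 10.3% | 48.5% |
| 3 | 0.3 | 5.6% | 1.9% | 14.3% | 28.6% |
| 3 | 0.6 | 3.5% | 1.6% | 16.7% | 16.7% |
| 4 | 0 | 10.0% | 1.2% | 8.0% | 59.8% |
| 4 | 0.3 | 4.7% | 1.0% | 12.8% | 35.7% |
| 4 | 0.6 | 2.6% | 0.8% | 15.8% | 20.9% |
| 5 | 0 | 10.0% | 0.7% | 6.5% | 67.3% |
| 5 | 0.3 | 4.0% | 0.5% | 11.9% | 40.5% |
| 5 | 0.6 | 2.0% | 0.4% | 15.3% | 23.6% |

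Share discharged before 48 hours: Φ(ln(2/3)/0.61) = 25%, Φ(ln(2/4)/0.61) = 13%, Φ(ln(2/5)/0.61) = 7%.

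**3. Cross-check with a simpler model.** Use is 1 unit per day for two days, then f per day, so the total is 2 + f(L − 2). With mean LOS 3 to 8 days and f = 0.25 to 1, a 10% shorter stay lowers the total by 3.3-10.0%, and a true 20% early effect shows as 5.0-17.8%. With L = 4 and f = 0.5 the total is 3.0. Both effects together give 1.6 + 0.5 × 1.6 = 2.4, a 20% fall, so here the two distortions cancel exactly. Over the grid the combined figure runs from 15.0% to 23.3%, on either side of the true 20%.

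**4. Effect on the test.** Simulation: 400 trials per setting, Wilcoxon test, 597 per arm (1514 / 1.266 / 2), median LOS 4 days, log-SD 0.5, log-SD of daily use 0.9. Results are for f = 0.25 / 0.5 / 1.

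- LOS 10% shorter, no opioid effect: p < 0.05 in 16 / 25 / 37% of trials for the total, against 8 / 6 / 6% for the 48-hour total. With no effect of any kind, the same simulation rejected in 5-8%.
- True 15% early reduction, LOS unchanged: power 59 / 44 / 25% for the total, against 86 / 83 / 85% for the 48-hour total.

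Monte Carlo standard error is up to about 2.5 points. Weekly clustering enters only through the effective sample size.

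**The case against.** The strongest reply is that the outcome matches the stated aim. The protocol asks about total inpatient opioid consumption, is motivated by opioid exposure and its in-hospital harms, and describes a pragmatic trial. For that question, fewer opioids through earlier discharge is part of the treatment effect, and the randomized comparison of totals is valid. This stands, so the total should stay. A reader might infer that it is the wrong outcome; the documents do not support that.

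A reader might also infer that a positive LOS result would all but guarantee an apparent opioid benefit. The figures do not bear this out. A 10% shorter stay alone made the total significant in only 16-37% of simulated trials. Among trials with a significant LOS result under the lognormal model, with the same MME spread and arm size, it was at most about 46%. A patient taking no opioids on the days removed contributes no fall at all.

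Nor should any claim of opioid sparing depend on the 48-hour result. An effect may outlast the infusion: protocol section 5 summarises a 24-hour infusion trial reporting differences in pain up to day 180. The total would capture a later in-hospital effect that a 48-hour window misses.

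Finally, a 48-hour window still closes early for patients discharged sooner, whom the SAP recognises in its per-protocol definition. The separation is therefore not complete.

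**Conclusion.** The point holds as a cheap improvement to a secondary outcome; the primary LOS analysis is unaffected. The total is valid for exposure but cannot by itself show whether ketamine lowered opioid need or shortened the time over which opioids were given, and no other planned analysis does so.

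The sizes in steps 2 to 4 rest wholly on assumed LOS and MME distributions. The share of MME given after 48 hours spans 17-67%, too wide to say that most of the total accrues after the infusion. A shorter stay inflates the apparent effect and later use dilutes the relative effect, so the documents do not support a claim of bias in a known direction. A shorter stay makes an apparent opioid benefit more likely, not certain.

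**What to change.** Keep total MME as defined. Add one prespecified supplementary outcome to the SAP: MME from anesthesia start to 48 hours after surgery, or to discharge if earlier, analysed with the same mixed-effect proportional odds model and covariates. Report the proportion discharged before 48 hours by arm.

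State how the two results will be read together: a lower total without a lower 48-hour total is described as fewer opioids during the stay, which may reflect a shorter stay or a later effect. Do not adjust for LOS instead, because it is itself a post-randomization outcome.

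The cost is one derived variable and a few lines of text. Protocol section 8 lists medication data and nursing records among the EMR sources; confirm that dose times are available in the extract. The downsides are one more secondary result and a truncated window for early discharges (about 7-25% under the assumptions above), which leaves a small residual dependence on LOS.
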